### **9.3 Characteristics of an Adverse Event**

#### ***9.3.1 Relationship to Study Intervention***

To assess relationship of an event to study intervention, the following guidelines are used:

1. Related (Possible, Probable, Definite)
  - a. The event is known to occur with the study intervention.
  - b. There is a temporal relationship between the intervention and event onset.
  - c. The event abates when the intervention is discontinued.
  - d. The event reappears upon a re-challenge with the intervention.
2. Not Related (Unlikely, Not Related)
  - a. There is no temporal relationship between the intervention and event onset.
  - b. An alternate etiology has been established.

#### ***9.3.2 Expectedness of SAEs***

We do not anticipate any serious adverse events related to the study intervention. The Study PI and co-investigator [name] will be responsible for determining whether an SAE is expected or unexpected. An adverse event will be considered unexpected if the nature, severity, or frequency of the event is not consistent with the risk information previously described for the intervention.

#### ***9.3.3 Severity of Event***

The following scale will be used to grade adverse events:

1. Mild: no intervention required; no impact on activities of daily living (ADL)
2. Moderate: minimal, local, or non-invasive intervention indicated; moderate impact on ADL

---

3. Severe: significant symptoms requiring invasive intervention; subject seeks medical attention, needs major assistance with ADL

## 9.4 Reporting Procedures

### 9.4.1 *Unanticipated Problem Reporting to IRB and PCORI*

Incidents or events that meet the criteria listed above for unanticipated problems require the creation and completion of an unanticipated problem report form. The following information will be included when reporting an adverse event, or any other incident, experience, or outcome as an unanticipated problem to the IRB:

- appropriate identifying information for the research protocol, such as the title, investigator's name, and the IRB project number;
- a detailed description of the adverse event, incident, experience, or outcome;
- an explanation of the basis for determining that the adverse event, incident, experience, or outcome represents an unanticipated problem;
- a description of any changes to the protocol or other corrective actions that have been taken or are proposed in response to the unanticipated problem.

To satisfy the requirement for prompt reporting, unanticipated problems will be reported using the following timeline:

- All unexpected problems involving risks to subject or others must be reported to the Case Western Reserve IRB within three (3) calendar days of discovery of the problem or event. The only exception to the above timeframe is for the reporting of deaths. All internal, unexpected, study-related deaths must be reported to the IRB as soon as the investigator learns of the event. Reporting to PCORI must also occur within 7 calendar days if death or a life-threatening event occurs or within 14 calendar days for all other SAEs.

For all reporting periods "days" refers to business days after the PI learned of the event. All reportable events need to be reported to the IRB within the timeline even if the information about the event is incomplete. Further information can be added with a follow-up report. All adverse events, including those reported to the study team must be promptly reviewed by the PI and any event that changes the risk/benefit ratio of the study, or requires a change in the protocol or the consent form, must be reported to the IRB within 3 business days.

- The PI and the study team must make the protocol changes as soon as possible and submit the revised documents to the IRB via the Amendment form
- Other events reported to CWRU IRB are as follows:
- All fatal events must be reported to the IRB as soon as the PI learns of the event, if the PI believes the event to be related to the study. If the death is determined to be unrelated to the study, it must be reported at the time of next Continuing Review.
- Deaths which occur after the subject's research participation has ended do not need to be reported to the IRB unless the death is related to study participation.
- All serious adverse events must be reported as soon as the PI learns of the event.

- All non-serious events and summary reports are kept in the PI's files and do not need to be reported to the IRB. The IRB does not require the PI to report adverse events that occur to subjects enrolled in an observational study or non-interventional study unless the event is related to study participation, causes a change in study design or increases risk for other participants.
- If a CWRU PI is notified about an event that occurred at another site in a study related to, but not the same as, the CWRU protocol, and the event results in a change in the protocol, consent form, or the risk/benefit ratio, the adverse event must be reported within 3 business days of learning of the event.
- If the change in the CWRU protocol is due to publication of results from another study which has an adverse impact on the CWRU protocol, it should be reported as soon as the PI learns of the valid publication.
- The PI who conducts research projects funded by a federal agency is obligated to report adverse events that are serious and unanticipated simultaneously to both the federal agency and to the IRB. The IRB has a separate and distinct obligation to report the adverse events to government authorities
- If the event changes the risk for other study participants and requires changes in the consent documents, report as soon as the PI learns of the event (but within 3 business days).
- Adverse events which occur in another study (including fatal events) and which do not result in a change in the protocol, consent form, or the risk/benefit ratio for the study, do not need to be reported to the IRB but should be kept on file by the PI.

#### **9.4.2 Serious Adverse Event Reporting to PCORI**

Any AE meeting the specified Serious Adverse Event criteria will be submitted on an SAE form to PCORI within 7 days. This report may be sent by fax or email. This process applies to both initial and follow-up SAE reports.

The PI will complete a Serious Adverse Event Form and submit via fax or email within the following timelines:

- All study-related deaths and immediately life-threatening events will be recorded on the Serious Adverse Event Form and submitted to Product Safety within 7 calendar days of site awareness.
- Study-related serious adverse events other than death and immediately life-threatening events, will be reported by fax within 14 calendar days of site awareness.

All SAEs will be followed until resolution or stabilization.

#### **9.5 Halting Rules**

It is not anticipated that there is a necessity for halting rules as the proposed study treatments are considered safe and approved by the FDA. But, all safety and adverse events data will be reviewed by the DSMB members. DSMB will review the interim analysis of the safety data and will give their recommendations every year.

## 10 STUDY OVERSIGHT

In addition to the PI's responsibility for oversight, study oversight will be under the direction of a Data and Safety Monitoring Board (DSMB) composed of members with appropriate clinical, statistical, scientific, and ethical expertise. PCORI will not appoint the Board as per their guidelines. But the study investigators would be responsible for the appointment of the DSMB. The DSMB will meet at least annually to assess safety and effectiveness data, study progress, and data integrity for the study. If concerns arise, more frequent meetings may be held. The DSMB will operate under the general rules of a NIH -approved charter that will be approved at the organizational meeting of the DSMB. The DSMB will provide recommendations to the study investigators and PCORI.

In addition to the PI's responsibility for oversight, study oversight will be under the direction of PCORI. The PI will submit a report every 6 months to the PCORI for review. This report will include data regarding enrollment and retention, unanticipated problems and protocol deviations, outcome measures, quality management findings and other relevant parameters. If necessary, additional steps may be taken to ensure data integrity and protocol compliance.

## 11 STATISTICAL CONSIDERATIONS

### 11.1 Study Hypotheses

This study tests the hypothesis that simple medical treatment (Arm 1) is non-inferior to typical dental treatment (Arm 2) for primary outcomes (caries arrest, tooth pain/hypersensitivity) and secondary outcomes (new decay, oral health quality of life) at 12-months post treatment.

### 11.2 Sample Size Considerations (RC-3)

For continuous outcomes we computed power using a variance correction (i.e., variance inflation factor) to take into account possible correlations of outcomes within cluster. All computations of required effective samples sizes (or corresponding power) were done using the PASS 2005 software. For binary outcomes, we used a specialized program for cluster randomization (a non-inferiority test comparing two proportions).

The primary outcome tooth pain was defined as change in pain (based on a 100-mm visual analogue pain scale (VAS), where higher is worse pain) from baseline to 1 year. We assume a mean difference of 0 between SDF and ART+FV, and consider non-inferiority to be within a margin (mean difference) of 8 between SDF and ART+FV arms; and based on prior literature also assume a common standard deviation of 25. Further, we assumed an average of 25 subjects recruited per site, an intraclass correlation (ICC) of 0.01 (based on prior studies and literature), and a 15% dropout rate (based on prior studies). The use of a 0.025 alpha-level one-sided t-test to test the null hypothesis of inferiority versus the alternative hypothesis of non-inferiority (as defined above), 11 sites per treatment group (corresponding to 275 subjects per treatment group or 550 total) will provide an estimated 89% power to conclude non-inferiority. Even if the ICC is higher (0.02), there will still be 83% power to detect non-inferiority.

A second primary outcome is arrest rate. Previous data show a high arrest rate (of around 90%) for ART + FV. We expect a similar arrest rate for SDF. For the power calculation we suppose the unit of analysis to be the person, and consider the binary outcome of 'arrest' defined as all lesions for an individual being arrested. We assume equal (person-level) arrest rates of 90% for the ART+FV and SDF groups, and consider non-inferiority to be within a margin (difference in arrest proportions for ART+FV versus SDF) of 0.09. With the same assumptions as before using a 0.025 alpha level one-sided z test, the targeted sample size of 275 subjects in 11 sites per treatment group will provide an estimated 85% power to conclude non-inferiority. For a higher ICC of 0.02, there will still about 80% power to detect non-inferiority.

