#### 3.2 Study Outcome Measures

##### 3.2.1 Primary Outcome Measures

Primary outcomes are: (1) participant reported outcomes including tooth pain and hypersensitivity, and (2) clinical outcomes (caries arrest). Clinical outcomes will be assessed through dental exams conducted by calibrated examiners. Participant questionnaire will assess patient-reported outcomes using validated instruments. All primary outcomes will be measured at baseline, 26 & 52 weeks.

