**Table 8.1.1 Quantitative Summary of measures, sources, and timeline (IR-4)**

Variable Type	Measure	Scale	Source	Timeline
Intervention by Study Arms	

• Biannual SDF (Arm 1)

• ART + biannual FV(Arm 2)

			$T_0, T_{26}$
Primary Outcome	Clinical dental exam 

• % freq of arrested surface/teeth

• Caries arrest

• overall score

		

• ICDAS Coronal and Root [Dikmen 2015]

	$T_0, T_{26}, T_{52}$

	Self-reported evaluation 
 
• Tooth pain/sensitivity
 
	
 
• overall score
 
	
 
• PROMIS v.1.0 - Pain Intensity 3a [Modified for Dental]
 
• Dental Discomfort Questionnaire [Modified for Adults from Versloot et al. 2006]
 
	T 0 , T 26 , T 52
Secondary Outcomes	Clinical dental exam 
 
• New decay
 
 Self-reported evaluation 
 
• OH-quality of life
 
	
 
• # freq of new decay teeth
 
• GOHRQoL overall score
 
	
 
• ICDAS Coronal and Root [Dikmen 2015]
 
• Geriatric Oral Health Quality of Life (GOHRQoL) [Atchison and Dolan, 1990]
 
	T 0 , T 26 , T 52 T 0 , T 26 , T 52
Process Outcome	
 
• Safety
 
• Satisfaction
 
	
 
• % freq. adverse event
 
• overall score
 
• overall score
 
	
 
• Safety Questionnaire (Pre- and Post-Exam/Treatment [Adapted for Adults from Milgrom et al. 2018]
 
• Treatment Satisfaction Questionnaire for Medication (TSQM) [Modified for Dental]
 
• Satisfaction with New Treatment for cavities [Modified for Adults from Crystal et al. 2017]
 
	T 0 , T 26 , T 52 T 52 T 52

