### 8.1.1 Quantitative outcomes of interventions

The primary (i.e., caries arrest, tooth pain / sensitivity) and secondary outcomes (i.e., presence of new decay, oral health-related quality of life) measure the effectiveness of the study interventions. The process outcome are to access the safety of the interventions and to ascertain patient satisfaction with the treatment 1 year after the initial treatment.

**Primary outcome: Older adults caries arrest and tooth pain / sensitivity (Arm 1: SDF vs. Arm 2: ART + FV) will be assessed through:**

- Clinical dental exam: will be performed at the two intervention time points (T0, T26) and final time point (T52) by a trained and calibrated dental hygienist according to the International Caries Detection and Assessment System II (ICDAS-II). The exam will be used to identify a change in oral health status between the Baseline visit and the 26-week visit (T0 and T26) as well as the 26-week visit and the 52-week visit (T26 and T52).
- Self-reported evaluation: Scales on tooth pain / sensitivity (PROMIS v.1.0, Health Organization; Dental Discomfort Questionnaire (DDQ)) will be used to measure levels of change in oral pain / sensitivity improvement. Higher scores on the PROMIS and DDQ

indicate increased tooth pain / sensitivity. These measures will be conducted during the baseline visit, 26-week visit, and 52-week visit ( $T_0$ ,  $T_{26}$ , and  $T_{52}$ ).

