## 11.4 Final Analysis Plan (IR-1, RC-4)

Each primary outcome will be compared between the SDF and ART+FV groups. For tooth pain, a 95% confidence interval (CI) based on a t-test for the difference in mean responses (SDF minus ART+FV) will be computed. If this confidence interval lies within the interval  $(-\infty, 8)$  we may conclude 'non-inferiority' of SDF relative to ART+FV treatment. The confidence interval may secondarily be examined to assess possible superiority of one intervention over the other. For arrest rate, a 95% CI for the difference in rates (based on a z statistic) will be computed. If this confidence interval lies within the interval  $(-0.09, 1)$  we may conclude 'non-inferiority' of the SDF relative to ART+FV treatment. As above, possible superiority of one intervention over the other may also be assessed. For other outcomes, we will also compute 95% CI for differences in means (or proportions for binary outcomes). These secondary outcomes will be assessed in an exploratory manner for possibly superiority or inferiority based on appropriate margins.

We will seek to corroborate initial results using a generalized estimating equations (GEE) approach. For each outcome we will fit a GEE (marginal) model that includes a treatment indicator and prognostic variables (including sociodemographic variables, medical conditions, and oral health behaviors). Appropriate link functions (e.g., logit link for binary outcomes and identity link for continuous outcomes) will be specified and an exchangeable working correlation matrix used to allow for correlations within site. The arrest outcome will be analyzed as a binary outcome (as described in the sample size section), and secondarily as the number of arrested lesions assuming an appropriate distribution (e.g., negative binomial) and link function (e.g., log link). Robust t tests with correction for a small number of clusters will be used to test for treatment effects and corresponding 95% confidence intervals computed.

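### The primary pain margin of 8, the SD of 25 and the 89% power belong to a 100-mm VAS, but the only pain measures the plan shows as collected are the modified PROMIS 3a and the modified DDQ

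*Combined protocol and SAP*

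**What the plan says.** Section 3.2.1 makes "participant reported outcomes including tooth pain and hypersensitivity" primary, alongside caries arrest. Section 11.2 then defines the pain variable for the power calculation as "change in pain (based on a 100-mm visual analogue pain scale (VAS), where higher is worse pain", taken from baseline to 1 year. On that scale it assumes no true difference, a margin of 8 and a common SD of 25, and it reports 89% power (83% at the higher ICC).

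Section 11.4 gives the decision rule. A 95% confidence interval "based on a t-test for the difference in mean responses (SDF minus ART+FV) will be computed", and SDF is non-inferior if the interval lies wholly below 8. This sentence mentions no instrument and does not mention change from baseline.

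The measurement sections describe something else. For tooth pain and sensitivity, Table 8.1.1 lists "PROMIS v.1.0 - Pain Intensity 3a [Modified for Dental" (closing bracket omitted) and the DDQ modified for adults, with the scale entered only as "overall score". Section 8.1.1 treats the two side by side ("Higher scores on the PROMIS and DDQ" both mean more pain or sensitivity). Appendix A schedules the same two instruments and no VAS. Outside section 11.2 the VAS appears only in the list of abbreviations.

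**The concern.** In a non-inferiority trial the margin defines the claim. Here one of the two primary margins is in millimetres of a VAS that the plan does not show as collected. No conversion to either collected score is given. An analyst following section 11.4 must therefore make two choices that the plan does not record: which score to test, and what 8 means on it.

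If 8 is carried over as a raw number, the margin is laxer than planned when the score's SD is below 25 and stricter when it is above. If the instrument is left open, it can be picked after the results are seen. If both scores are tested, error and power depend on a combination rule that is not written down. The caries-arrest rule is unaffected.

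**Working it through.** **Inputs (section 11.2).** One-sided alpha 0.025 (z = 1.96); 275 per arm in 11 sites per arm; 25 per site; dropout 15%; ICC 0.01 or 0.02; margin 8; SD 25; true difference 0.

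**Step 1: reproduce the stated power.**
- Completers per arm: 275 × 0.85 = 233.75. Completers per site: 25 × 0.85 = 21.25.
- Design effect = 1 + (21.25 − 1) × ICC = 1.2025 at ICC 0.01 and 1.405 at ICC 0.02.
- Effective n per arm = 233.75 / design effect = 194.4 and 166.4.
- SE = 25 × √(2 / effective n) = 2.536 and 2.741.
- Power = Φ(8/SE − 1.96) = 88.4% and 83.1%, against 89% and 83% stated.

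The calculation reproduces. It depends on the scale only through margin/SD = 8/25 = 0.32.

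**Step 2: keep 8, change the scale.** The documents give no SD for either collected score, so the SDs below are assumptions (ICC 0.01). SE = SD × √(2/194.4). The last column is Φ((8 − 0.32 × SD)/SE − 1.96): the chance of declaring non-inferiority when SDF is truly 0.32 SD worse, which is the tolerance implied by section 11.2.

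| Assumed SD of change | 8 in SD units | Power, no true difference | Declared non-inferior when SDF is 0.32 SD worse |
|---|---|---|---|
| 10 | 0.80 | >99.9% | 99.7% |
| 15 | 0.53 | >99.9% | 56% |
| 20 | 0.40 | 97.6% | 12% |
| 25 | 0.32 | 88% | 2.5% |
| 30 | 0.27 | 75% | 0.6% |
| 40 | 0.20 | 50% | 0.1% |

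**Step 3: two scores, none designated.** Assume that each score has margin/SD 0.32 and that the two test statistics are bivariate normal with the correlation shown.

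| Correlation | One-sided error if either may carry the claim (both at the margin) | Power if both must pass (no true difference) |
|---|---|---|
| 0 | 4.9% | 78% |
| 0.5 | 4.5% | 81% |
| 0.9 | 3.5% | 85% |

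A single designated score gives 2.5% and 88%.

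**Step 4: power for a re-stated margin.** At ICC 0.01, by ratio of margin to SD of change:

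| Design | 0.25 | 0.30 | 0.32 | 0.40 |
|---|---|---|---|---|
| 550 participants, 22 sites (as in section 11.2) | 69% | 84% | 88% | 98% |
| 590 participants, 26 sites (section 4.2 modification) | 73% | 87% | 91% | 98% |
| 590 participants, 33 sites (Protocol Summary, Table 1) | 74% | 88% | 92% | 99% |

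**The case against.** The strongest reply is that section 11.2 is a definition and section 11.4 borrows from it. On that reading the variable, time point, direction, margin and test are all prespecified, and the only gap is how the VAS variable maps to the questionnaires. Both instruments are labelled as modified and the forms are not in the documents, so one of them may use a 0-100 format. The fix would then be a labelling correction. The error and power figures also rest on assumed SDs, on 8 being applied unchanged, and on reading the margin as 0.32 SD, whereas section 11.2 states it only in VAS points. Zero correlation between two self-reports of tooth pain is implausible, and Table 8.1.1 could mean one combined score.

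Some of this stands. A 0-100 format cannot be excluded. The tables above show what could happen and do not measure what will, and the realistic two-score effect is near the mild end (3.5% error or 85% power at correlation 0.9). But reading section 11.4 through section 11.2 ties the limit of 8 more firmly to a scale that no schedule shows. A 0-100 format or a combined score would each have to be stated, and neither is. A 0-100 format would also leave two instruments with no designated primary.

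**Conclusion.** The point holds and needs correcting before the pain analysis. The arithmetic behind 89% is right. What is wrong is that a primary decision limit and its power are stated for a variable the plan does not show as collected, with no margin, SD or choice of score for the variables it does show. The planned 2.5% error and 88% power carry over only if the score tested has an SD of change of about 25 in its own units, or if the limit is reset to about 0.32 SD. Departures can be large: at an assumed SD of 20 the 2.5% becomes 12%, and at an assumed SD of 30 power becomes 75%. These sizes assume that 8 is kept as a raw number, ICC 0.01 and the section 11.2 sample size. Using the enlarged sample of 590 moves the 88% only to 91-92%.

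**What to change.** Before any outcome comparison by arm, revise sections 11.2 and 11.4:

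1. Name one collected pain score, or a fully specified combination, as the primary pain variable. Define it as change from baseline to the 52-week assessment and make the other score supportive. State its range and scoring.
2. Replace 8 with a margin justified as a tolerable difference in that score's units. Replace 25 with an SD of the change score, for example the SD of change pooled over both arms without treatment labels. Choose the margin on clinical grounds and not to recover a ratio of 0.32.
3. Restate power from the new ratio, using the current sample size and site count.
4. Put the score's name, the words change from baseline and the new limit into the confidence-interval rule in section 11.4.
5. If a VAS or a 0-100 format is in fact collected, say so in Table 8.1.1, section 8.1.1 and Appendix A, and state which score carries the test.

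The cost is protocol and SAP wording, one blinded SD calculation and a written margin justification. No new data and no new participants are needed. If arm-level pain results have already been seen, the revision should say so and date the choice.
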